13.6.4. Missing Severity Assessment for Adverse Events

- If severity is missing for an AE starting prior to the date of study day 1, then a severity of "Mild" will be assigned.
- If the severity is missing for an AE starting on or after the date of study day 1, then a severity of "Severe" will be assigned.

The imputed values for severity assessment will be used for incidence summaries, while the actual values will be presented in data listings.

13.6.5. Missing Relationship to Investigational Product for Adverse Events

If the relationship to investigational product is missing for an AE starting on or after the date of study day 1, a causality of "related" will be assigned. The imputed values for relationship to double-blind investigational product will be used for incidence summaries, while the actual values will be presented in data listings.

13.6.6. Character Values of Clinical Laboratory Variables

If the reported value of a clinical laboratory variable cannot be used in a statistical analysis due to, for example, that a character string is reported for a numerical variable. The appropriately determined coded value will be used in the statistical analysis. If the laboratory results are collected as < or > a numeric value, 0.0000000001 will be subtracted or added, respectively to the value. However, the actual values as reported in the database will be presented in data listings.

14. ANALYSIS SOFTWARE

Statistical analyses will be performed using Version 9.4 (or newer) of SAS on a suitably qualified environment.

15. CHANGES TO ANALYSIS SPECIFIED IN PROTOCOL

Not applicable.

17. APPENDICES

17.1. Schedule of Assessments

Study period	Scree	ening iod ²			Randor	mized co	ontrolle	l period				(Follow-up period					
Study week	-10 to -4	-2	1	4	8	12	16	20	24	26	28	32	36	42	48	52	54	56	60 Exit
Study day	-70	-14	1	28	56	84	112	140	168	182	196	224	252	294	336	364	378	392	420
Study visit	1	2	3	4	5	6	7	8	9	10	11	12	13	14	15	16	17	18	19
Visit window (± days)	N/	Ab	0	3	7	7	7	7	3	3	3	7	7	7	7	7	3	3	7
							Assessn	nents						00					
Informed consent	X																		
Demographics	X									j.		,							
Medical history	X												,						
Post-transplant immunosuppression plan documentation		x																	
Inclusion/exclusion	x	x	x																
Vaccination ^d		\mathbf{X}_{p}				X													
Adverse events	x	X	x	x	х	x	x	x	x	x	x	x	x	x	x	x	x	x	x
Concomitant medications	X	X	X	X	х	x	X	x	x	x	х	x	X	х	X	X	х	X	X
Physical examination (full) ^e	X		X							Xe						X			
Physical examination (brief) ^e		X		X	х	х	х	х	х		Xe	х	X	х	Х		х	X	х
12-lead ECG	X		X		X		х		x	x	х		X		х	X	X		X
Chest radiography		Χb								х						х			
Renal biopsy ^f)	C _p								Xg						Xh			
Randomization			X																
Study drug administrationi			X	X	X	X	X	X	X	X	X	X	X	X	X	X			
Infusion site/pump safety assessment			x	x	x	x	x	х	x	x	x	x	x	x	X	x	х		
Vital sign measurementsk	X	X	X	X	X	X	X	X	X	X	X	X	X	X	X	X	X	X	X
HRQoLl		X								x						x			

Study period		ening iod ^a	Randomized controlled period								(Follow-up period						
Study week	-10 to -4	2	1	4	8	12	16	20	24	26	28	32	36	42	48	52	54	56	60 Exit
Study day	-70	-14	1	28	56	84	112	140	168	182	196	224	252	294	336	364	378	392	420
Study visit	1	2	3	4	5	6	7	8	9	10	11	12	13	14	15	16	17	18	19
Visit window (± days)	N/	Ab	0	3	7	7	7	7	3	3	3	7	7	7	7	7	3	3	7
							Urii	1e											
24-hour urine collection ^m	X					X			X		8	27	X		X				X
Triplicate FMU uPCR ⁿ	x	x	Χ°	x	x	x	x	x	x	x	x	x	x	x	х	x	x	x	x
In-clinic (random) uPCR	X	X	X	X	X	X	X	X	X	X	X	X	X	X	X	X	X	X	X
Urinalysis (dipstick & microscopic) ^p	x																		
Urine pregnancy test		X	X	X	X	X	x	X	X	X	X	X	X	X	X	X	X	X	X
							Bloc	od											
Hematology ^p & chemistry ^p	X	X	X	X	X	X	X	X	X	X	X	X	X	X	X	X	X	X	X
PK sample collection			x	x	x	x	x	x	x	X	x	x	x	X	x	x	x	X	x
ADA assaysq			X	X			X		X			v.:	X			X	X		X
Serum complement profilep	X	X	X	X	X	x		x	X	x	X	X	X		X	X	X	X	X
Plasma complement profile ^p	x		X		X		X		X	X	X		X		X	X	X		X
eGFRr	X	X	X	X	X	X	x	X	X	X	X	x	X	X	X	X	X	X	X
Pregnancy (β-HCG)	X																		
Screening assayss	X																		
						Opt	ional as	sessmen	ts										
Ophthalmologic evaluations ^t		Xt												Xt					
Measured GFR ^u			Xu							Xu				Xu					

Abbreviations: Ab = antibodies; ADA = antidrug antibodies; AE = adverse events; AH50 = 50% alternative hemolytic complement pathway activity, ANA = antimelear antibodies; ANCA = antineutrophil cytoplasmic antibodies; BHCG = beta human chorionic gonadotropm, CH50 = 50% classical hemolytic complement pathway activity, ECG = electrocardiogram, eGFR = estimated glomerular filtration rate; EQ-5D-SL = 5-Level EuroQol-5 Dimension; FACIT-Fatigue = Functional Assessment of Chronic Illness Therapy-Fatigue Scale; FMU = first-morning spot urine; FSH = follicle-stimulating hormone; GFR = glomerular filtration rate; HIV = human immunodeficiency virus; HRQoL = health-related quality of life; KDQOL = Kidney Disease Quality of Life; N/A = not applicable; PGIC = Patient Global Impression of Change; PK = pharmacokinetic; SC = subcutaneous; SD OCT = spectral domain optical coherence tomography; SPEP = serum protein electrophoresis; uPCR = urine protein-to-creatinine ratio; WPAI = Work Productivity and Activity Impairment.

NOTE: When multiple assessments/procedures occur at the same visit, order should be: vital signs, ECGs, blood collection/sampling, study drug dosing.

Pegcetacoplan (APL-2) APL2-C3G-310 Statistical Analysis Plan Version 2.0

27 June 2024

- All visit 2 assessments need not occur in a single visit and visit 2 can be split into multiple visits (eg, visit 2a, visit 2b).
- Vaccinations, baseline renal biopsy, and screening chest radiography can occur any time during screening after confirmation of eligibility based on visit 1 data.
- For transplant participants only. Must be documented prior to assignment to study treatment.

 Vaccine series should be initiated at least 14 days prior to randomization; additional vaccines may be required at visit 6. Please see Protocol Section 8.2 for more details on vaccination requirements. Vaccination serum samples will be collected on the day of vaccination before receiving vaccinations on that visit. These samples will be analyzed to evaluate response to vaccinations in the event that the participant has a positive infection for Streptococcus pneumoniae, Neisseria meningitidis, or Haemophilus influenzae.
- A full physical examination is required at visits 1, 3 (week 1), 10 (week 26), and 16 (week 52). A full physical examination should also be conducted on the first day of open-label dosing, if that is not at the week 26 visit. Brief physical examinations, including weight (kg) and assessment of edema, will be conducted at all other visits noted. A symptom-driven physical examination may be performed at any time, at the investigator's discretion. Body height (cm) will be measured only during screening for adults but will be measured at screening and every 12 weeks throughout the study for adolescents; weight (kg) will be measured throughout study, during brief and full physical examinations for all participants. Both body weight and height will be assessed without shoes on; height will be measured using a calibrated stadiometer. Edema should be assessed at every visit.

 Renal biopsies will not be required for participants younger than 18 years provided that they have adequate previous renal biopsies to establish the diagnosis as per the central pathology laboratory.
- The week 26 renal biopsy need not occur on the same day as all other assessments for that visit. However, the week 26 triplicate FMU uPCR collections must occur before the renal biopsy. In addition, the week 26 biopsy must occur before the first visit of the open-label period at week 28. Participants younger than 18 years are not required to provide renal biopsies and may advance to
- the open-label period upon completion of all assessments for weeks 24 through 26 other than the renal biopsy.

 The week 52 renal biopsy is optional for all participants. If performed it should be after collection of the week 48 24-hour urine and FMU samples, and not more than 8 weeks after the week 52 visit. In the event that a participant has a renal biopsy as part of their clinical management within this window, it may serve as the week 52 biopsy provided that it includes the required components for
- Study drug will be self-administered by the participant or administered by their caregiver, after receiving appropriate training and sign-off by a research nurse (or other qualified personnel) in their first treatment week, as described in Protocol Section 9.5. Once qualified, the participant or caregiver should administer study drug at site visits (as done at home) on those days when a clinic visit occurs on a dosing day. If a home nurse is administering study drug on nonvisit days, the site staff may administer study drug on days of site visits.
- Between site visits, participants will be instructed to report any infusion site reactions to the study staff. Pump use safety will be reviewed by licensed health care professionals (eg, investigator or nurse) for each study drug administration at clinic visits and during at-home qualification.
- Vital signs should be measured a maximum of 2 hours before study drug infusion. On day 1 and on the first day of open-label dosing (week 26 or week 28, depending on whether a week 26 renal biopsy is required and when it is performed), vital signs should also be measured approximately 30 minutes to 1 hour after the first infusion of study drug dosing, timed from the completion of the study drug administration. Blood pressure and heart rate should be evaluated after the participant has been resting in a seated position for at least 5 minutes, except when they are supine or semireclined because of study procedures and/or AEs, or if deemed necessary by the investigator
- FACIT-Fatigue, EQ-5D-5L, KDQOL, PGIC, and WPAI.
- The screening 24-hour urine collection may be done any time between screening visit 1 and screening visit 2. After week 1, collections should be within ±1 week of the visit (except for the week 24 collection, which cannot be earlier than week 24). Courier arrangements can be made to pick up the collection container from the participant, or the participant may return the container directly to
- Triplicate FMU samples will be collected by the participant at home on 3 consecutive days throughout the duration of the study. These should be the first urinary output of the day. An additional triplicate FMU uPCR sample will be collected at week 25. Samples should be collected within ±1 week of the clinic visit (except for weeks 24 through 26, when sample collection should be within ±3 days of the clinic visit). Courier arrangements can be made to pick up the collection containers from the participants, or the participant may return the containers directly to the site. At every visit, enough uPCR collection containers should be dispensed to the participant to enable all at-home uPCR collections until the next clinic visit.
- The day 1 triplicate FMU uPCR samples should be collected before the first dose of study drug (eg, day -2, day -1, and before dosing on day 1).

 Serum complement profile includes AH50, CH50, and C3NeF; C3NeF will only be assayed in samples collected at the baseline (screening) visits. Plasma complement profile includes C3a,
- C3b/iC3b, C5a, and sC5b 9. See laboratory assessments (Protocol Table 4) for more details.

 The day 1 samples should be collected before dosing with study drug. Participants who discontinue dosing will have ADA samples collected at 2 and 8 weeks after the last treatment. Participants
- who have a treatment-emergent or treatment-boosted ADA response at any time will have ADA samples collected approximately every 6 months until the antibody levels revert to baseline. eGFR will be calculated using the Chronic Kidney Disease–Epidemiology Collaboration creatinine equation for adults or the Bedside Schwartz equation for adolescents. For each participant, eGFR will be calculated using the same formula for the duration of the study; the choice of formula will be determined by the participant's age at study entry
- Serum FSH (to be measured in female participants only), hepatitis B panel, hepatitis C panel, HIV antibodies, SPEP (adult participants only), ANA, and ANCA (see Protocol Table 4 and laboratory manual for more details).
- Ophthalmologic evaluations are optional and will be performed at selected sites. If evaluations are performed, each participant should have a baseline ophthalmologic evaluation, including a basic ophthalmologic examination, SD-OCT, and color fundus photography, at an approved ophthalmologic clinical site at any time during the screening period. For participants who have drusen before pegcetacoplan administration, a follow-up ophthalmologic evaluation, including an SD-OCT and color fundus photography, should occur at a convenient time between weeks 44 and 52.
- Measured GFR is an optional assessment that, if performed, should occur at 3 time points: once on day 1 or within 10 weeks before day 1, again at week 26, and a third time between week 44 and week 52, inclusive. Measured GFR should only be done at sites where it is routinely performed, as per the site's standard protocol.

17.2. Sample SAS code

```
* The SAS codes in this section are shown as examples
* Some modifications (such as variables used in the model statement)
* may require further changes to reflect the methods specified in the
* SAP and analysis data structure
```

17.2.1. Mixed Effect Model for Repeated Measure

```
*_____
* Read Analysis data
* In this example, repeated measures are available at
* avisitn = 0 (baseline), 4 (Week 4), 8 (Week 8), 12 (Week 12), 16 (Week 16),
  20 (Week 20), 24 (Week 24), 25 (Week 25), and 26 (Week 26)
data upcr;
 set adam.adeff;
 if paramcd = 'LNUPRCRF' and basetype = 'NORMAL' and
 avisitn in (0, 4, 8, 12, 16, 20, 24, 25, 26) and
 ANLO1FL = 'Y';
 * avisitc will be used in PROC TRANSPOSE;
 if avisitn = 0 then avisitc = '00'; * Baseline;
 if avisitn = 4 then avisitc = '04'; * Week 4;
 if avisitn = 8 then avisitc = '08'; * Week 8;
 if avisitn = 12 then avisitc = '12'; * Week 12;
 if avisitn = 16 then avisitc = '16'; * Week 16;
 if avisitn = 20 then avisitc = '20'; * Week 20;
if avisitn = 24 then avisitc = '24'; * Week 24;
if avisitn = 25 then avisitc = '25'; * Week 25;
if avisitn = 26 then avisitc = '26'; * Week 26;
**********
*** ANALYSIS using MMRM assuming MAR (e.g., Section 6.4.2(1) )***;
proc sql;
     select avg(base) into: abs
     from upcr t; * upcr t is the upcr dataset but in long format;
run;
%put abs=&abs; * this will be used for the "estimate" statement, similarly
to obtain the empirical weight for each stratification factor and disease
type and baseline immune use, namely stra1_wt, stra1_wt_rev, stra2_wt,
stra2 wt rev, distype wt, distype wt rev, immunobl wt, immunobl wt rev to be
used in next procedure;
proc mixed data=upcr method=reml covtest empirical;
 where avisitn NE 0; * exclude rows for baseline;
  * stra1 (stratification factor 1)
  * 0 = post-transplant recurrence
  * 1 = non-transplant
```

```
* stra2 (stratification factor 2)
 * 0 = Without Baseline Renal Biopsy
 * 1 = With Baseline Renal Biopsy
 * distype (disease type)
 * 0 = IC-MPGN
 * 1 = C3G
 * immunobl (baseline immunosuppressants use)
 * 0 = No
 * 1 = Yes
 class trtpn avisitn usubjid stra1 stra2 distype;
 model chg = trtpn stra1 stra2 distype immunobl avisitn trtpn*avisitn
base/cl;
 repeated avisitn / subject=usubjid type=un r;
 lsmeans trtpn*avisitn/pdiff cl e om alpha=.05;
 ods output diffs= diff1 LSMeans= LSMean1;
estimate 'PEG Week 24-25-26 Avg LSMean' intercept 1 stral &stral wt rev
&stral wt stra2 &stra2 wt rev &stra2 wt distype &distype wt rev
&distype wt immunobl &immunobl wt rev &immunobl wt trtpn {\bf 1} {\bf 0}
BASE &abs
avisitn 0 0 0 0 0 0.333 0.333 0.334
trtpn*avisitn 0 0 0 0 0 0.333 0.333 0.334
           0 0 0 0 0 0 0 0 /cl ;
estimate 'PEG vs PBO Difference Week 24-25-26 Avg' trtpn 1 -1
trtpn*avisitn 0 0 0 0 0 0.333 0.333 0.334
           0 0 0 0 0 -0.333 -0.334 /cl ;
ods output estimates = est;
run;
data lsmeans1;
set lsmeans;
LS Geometric mean;
LS Geometric mean;
run;
data diffs1;
set diffs;
geo lower = exp(lower);
                             * = lower bound of the 95%CI for the
LS Geometric mean ratio;
                             * = upper bound of the 95%CI for the
geo upper = exp(upper);
LS Geometric mean ratio;
run;
data est1;
set est;
geo lower = exp(lower);
geo upper = exp(upper);
run;
```

17.2.2. Multiple Imputation

```
**********
*** MAIN ANALYSIS (e.g., Section 6.4.1 ) ***;
*********
***********
*** RESHAPE DATA FOR PROC MI ***;
**********
proc sort data= upcr;
by usubjid stra1 stra2 distype immunobl trtpn base avisitc;
run;
by usubjid stra1 stra2 distype immunobl trtpn base;
id avisitc;
var aval;
run:
* Examine the missing patterns of the data;
proc mi data=upcr t nimpute=0;
var stra1 stra2 distype immunobl trtpn v00 - v26;
ods output missPattern=pattern;
run:
***********
*** MCMC (impute nonmonotone missing) ***;
************
* Below statements invoke MCMC procedure and specify IMPUTE=MONOTONE
to turn the arbitrary missing patterns to monotone missing patterns
under missing at random (MAR) assumption;
proc mi data=upcr t out=upcr t mono seed=
                                         nimpute=100;
mcmc chain=multiple impute= monotone disp
   initial=em(itprint);
var stra1 stra2 distype immunobl trtpn v00 - v26;
run;
* Examine the missing patterns of the data;
proc mi data=upcr t mono nimpute=0;
var stra1 stra2 distype immunobl trtpn v00 - v26;
ods output missPattern=pattern;
run:
**********************
*** Control-based pattern imputation(impute monotone missing) ***;
data upcr_t_mono2;
     set upcr t mono;
     **Identify the subjects in the active groups we want to keep
 imputed as MAR;
    if ICEDT1>. or ICEDT2>. or ICEDT3>. then MAR = 'N';
     else MAR = 'Y';
    if trt01 = 2 then MAR = 'N';
```

```
**First impute general MAR based on regression method for all subjects to get
the true MAR;
proc mi data=upcr t mono2 out=upcr step1 nimpute=1 seed=
by Imputation;
class trtpn;
monotone reg(v00 - v26/details);
var stra1 stra2 distype immunobl trtpn v00 - v26;
run;
**Identify and keep the data from the subjects in the active group that
should remain as a MAR;
data upcr step2;
      set upcr step1;
      if Mar = "Y";
      run;
**Update the dataset and keep the MAR imputed data for the subjects in the
active group that should remain as a MAR, all others remain to be imputed
with control based imputation;
data upcr t mono3;
      update upcr t mono2 upcr step2;
      by Imputation subjid;
      run:
**Fill out the remaining missing where missing data should be imputed based
on the controls;
proc mi data=upcr t mono3 out=upcr t cbp nimpute=1 seed=
 by imputation;
class trtpn;
var stra1 stra2 distype immunobl v00 - v26;
monotone reg(/details);
mnar model(v04 - v26 / modelobs= (trtpn='2'));
run;
**if there are ICEs of renal transplant/dialysis (ICEDT2>.) then need to
impute based on worst change;
** first, transpose the above upcr t cbp back to long format upcr cbp(omit
the details), then, collect details on worst percentage across all visits
based on original data (e.g., name the variable as worstpchg), also, identify
for those subjects who had ICEDT2>., their first visit that should be imputed
based on worst percent change (e.g., name the variable as startavisit), plus,
for all 100 imputations, calculate the average log(uPCR) for each avisit
(e.g., name the variable as visit_avg), then;
data upcr cbp worst;
      merge upcr cbp worstpchg startavisit visit avg;
      by subjid;
      if avisitn>startavisit>. then aval = base*(1+ worstpchg/100) + (aval-
visit avg);
      **Note, the "base*(1+ worstpchg/100)" part is worst change, the "(aval-
visit avg)" is random error;
      run;
** lastly, transpose it back to the wide format;
```

```
proc transpose data= upcr cbp worst out= upcr t cbp worst (drop= NAME
_LABEL_) prefix=V;
by usubjid stra1 stra2 distype immunobl trtpn base;
id avisitc;
var aval;
run;
*******************
*** Delta-Adjusted Pattern Imputation (tipping point analysis) ***;
************************
**First identify the subjects in the active treatment groups that we want to
apply the shift parameter if they have monotone missing data;
data upcr t mono2;
     set upcr t mono;
     **ICEDT1=. is just an example of a reason that we do not want to
 apply the shift parameter. The actual reasons are in the text;
     if ICEDT1=. then flag = 1;
     else flag = 0;
     if trtpn = 1 and flag = 0 then adjustthis = 1;
     else adjustthis = 0;
run:
proc mi data=upcr t mono2 out=upcr t tip nimpute=1 seed=
by imputation;
class trtpn adjustthis;
var stra1 stra2 distype immunobl trtpn v00 -- v12;
monotone reg(/details);
mnar adjust(v04 / shift=0.04 adjustobs=(adjustthis = '1' ))
 adjust(v08 / shift=0.04 adjustobs=(adjustthis = '1'))
 adjust(v12 / shift=0.04 adjustobs=(adjustthis = '1' ))
 adjust(v16 / shift=0.04 adjustobs=(adjustthis = '1' ))
 adjust(v20 / shift=0.04 adjustobs=(adjustthis = '1'))
 adjust(v24 / shift=0.04 adjustobs=(adjustthis = '1'))
 adjust(v25 / shift=0.01 adjustobs=(adjustthis = '1'))
 adjust(v26 / shift=0.01 adjustobs=(adjustthis = '1'));
run;
***************
*** SAS macro to run MIANALYZE on outputs from MMRM *;
*****************
%macro mi results(in, lsm, dif); ** Note this macro is for individual visits
such as W4, W8,..., W24, W25, W26, see next macro for composite contrast of W24-
W25-W26 average;
proc transpose data= &in
   out= upcr mi (rename= ( NAME = AVISITN COL1 = AVAL));
by imputation usubjid trtpn base stra1 stra2 distype immunobl;
```

```
var V00 - V26;
run;
data upcr mi;
set upcr mi;
label AVISITN = 'AVISITN';
 chg = aval - base;
  * baseline record is not used in MMRM;
 if AVISITN = 'V00' then delete;
run:
proc sort; by imputation; run;
proc mixed data=upcr mi method=reml covtest empirical;
by imputation;
class trtpn avisitn usubjid stra1 stra2 distype immunobl;
model chg=trtpn stra1 stra2 distype immunobl avisitn trtpn*avisitn base /cl;
repeated avisitn / subject=usubjid type=UN;
lsmeans trtpn*avisitn / pdiff cl om alpha=.05;
ods output diffs= diffs lsmeans= lsmeans;
run;
* In the final step, the analysis results obtained from PROC MIXED
 procedure are combined into a single estimation with standard error
  using PROC MIANALYZE;
proc sort data=lsmeans;
by avisitn trtpn _imputation_;
run;
proc mianalyze parms=lsmeans;
by avisitn trtpn;
modeleffects trtpn*avisitn;
ods output ParameterEstimates=&lsm;
proc sort data=diffs (where= ( trtpn= 2 and (avisitn = avisitn)));
by avisitn trtpn trtpn imputation;
run;
proc mianalyze parms=diffs;
by avisitn trtpn _trtpn;
modeleffects trtpn*avisitn;
ods output ParameterEstimates=&dif;
proc sql; *** LSMEANS using Multiple Imputation;
  select Parm as Effect, AVISITN, TRTPN, Estimate, StdErr, DF,
   tValue, Probt, LCLMean as L95, UCLMean as U95
 from &lsm;
  select Parm as Effect, AVISITN, TRTPN, TRTPN, Estimate, StdErr, DF,
    tValue, Probt, LCLMean as L95, UCLMean as U95
 from &dif;
quit;
%mend;
%mi_results(in= upcr_t_cbp, lsm= lsm_cbp, dif=dif_cbp );
```

APL2-C3G-310 Statistical Analysis Plan Version 2.0

```
%mi results(in= upcr t cbp worst, lsm= lsm cbp, dif=dif cbp );
%macro mi results(in, lsm, dif); ** Note this macro is for composite contrast
of W24-W25-W26 average;
proc sql;
      select avg(base) into: abs
     from &in
      group by imputation;
%put abs=&abs; * this will be used for the "estimate" statement, similarly
to obtain the empirical weight for each stratification factor and disease
type, namely stra1 wt, stra1 wt rev, stra2 wt, stra2 wt rev, distype wt,
distype wt rev, immunobl wt, immunobl wt rev to be used in next procedure;
proc transpose data= &in
   out= upcr mi (rename= ( NAME = AVISITN COL1 = AVAL));
by imputation usubjid trtpn base stral stra2 distype immunobl;
var V00 - V26;
run;
data upcr mi;
set upcr mi;
 label AVISITN = 'AVISITN';
 chg = aval - base;
 * baseline record is not used in MMRM;
if AVISITN = 'V00' then delete;
run:
proc sort; by imputation; run;
proc mixed data=upcr mi method=reml covtest empirical;
by imputation;
 class trtpn avisitn usubjid stra1 stra2 distype immunobl;
model chg=trtpn stra1 stra2 distype immunobl avisitn trtpn*avisitn base /cl;
 repeated avisitn / subject=usubjid type=UN;
 lsmeans trtpn*avisitn / pdiff cl alpha=.05 om;
estimate 'PEG Week 24-25-26 Avg LSMean' intercept 1 stral &stral_wt_rev
&stra1_wt stra2 &stra2_wt_rev &stra2_wt distype &distype_wt_rev &distype_wt
immunobl & immunobl wt rev & immunobl wt trtpn {f 1} {f 0}
BASE &abs
avisitn 0 0 0 0 0 0.333 0.333 0.334
trtpn*avisitn 0 0 0 0 0 0.333 0.333 0.334
              0 0 0 0 0 0 0 0 /cl;
estimate 'PEG vs PBO Difference Week 24-25-26 Avg' trtpn 1 -1
trtpn*avisitn 0 0 0 0 0 0.333 0.333 0.334
               0 0 0 0 0 -0.333 -0.334 /cl ;
  ods output estimates = est;
run;
proc mianalyze data=est(where=(label='PEG Week 24-25-26 Avg LSMean'));
 modeleffects estimate;
 stderr stderr;
  ods output ParameterEstimates=&lsm;
run;
```

```
proc mianalyze data=est(where=(label='PEG vs PBO Difference Week 24-25-26
Avg'));
 modeleffects estimate;
 stderr stderr;
 ods output ParameterEstimates=&dif;
proc sql; *** LSMEANS using Multiple Imputation;
  select Parm as Effect, Estimate, StdErr, DF,
       tValue, Probt, LCLMean as L95, UCLMean as U95
    from &lsm;
  select Parm as Effect, Estimate, StdErr, DF,
       tValue, Probt, LCLMean as L95, UCLMean as U95
    from &dif;
quit;
%mend;
%mi_results(in= upcr_t cbp, lsm= lsm_cbp, dif=dif_cbp );
%mi_results(in= upcr_t_cbp_worst, lsm= lsm_cbp, dif=dif_cbp );
```

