6.3. Estimands

The primary objective of this study is to assess the efficacy of twice-weekly SC doses of pegcetacoplan compared with that of placebo in patients with primary C3G or IC-MPGN on the basis of a reduction in proteinuria.

The estimands and their attributes for the primary and all comparative key secondary and additional secondary endpoints are shown in Table 1 below. This includes strategies for addressing the following intercurrent events (ICEs):

- ProhibiRescue = use of prohibited concomitant medication specified in Protocol Section 8.3.3, or use of rescue therapies defined in Protocol Section 8.3.2
- RenalReplace = start renal replacement therapy (dialysis and/or renal transplant)
- DisctTrt = permanent discontinuation of study treatment

Table 1: Estimands and Attributes for Primary, Key Secondary, and Additional Secondary Endpoints

Socona	Secondary Endpoints				
For all estimands: A. Population: participants with C3G or IC-MPGN defined through the study inclusion/exclusion criteria in the ITT Set B. Treatment regimens of interest: • Twice-weekly SC doses of pegcetacoplan for 26 weeks of treatment • Twice-weekly SC doses of placebo for 26 weeks of treatment					
C: Variable (or endpoint) D: Strategies for addressing ICEs (event†: strategy‡) E: Population-level sum					
Primary Estimand					
Log-transformed ratio of uPCR at week 26 compared to baseline	ProhibiRescue: hypothetical strategy RenalReplace: hypothetical strategy DisctTrt: treatment policy strategy	Difference in mean change of log-transformed uPCR from baseline to week 26 (measured by equal-weighted average over weeks 24, 25, and 26) between the pegcetacoplan group and the placebo group.			
Key Secondary Estimands	(for comparative endpoints)				
The proportion of participants who meet the criteria for achieving a composite renal endpoint at week 26	ProhibiRescue, RenalReplace, DisctTrt: composite strategy	Odds ratio of achieving a composite renal endpoint for the pegcetacoplan group to achieving a composite renal endpoint for the placebo group at week 26.			
The proportion of participants with a reduction of at least 50% from baseline in uPCR at week 26	ProhibiRescue, RenalReplace, DisctTrt: composite strategy	Odds ratio of achieving a reduction of at least 50% from baseline in uPCR for the pegcetacoplan group to achieving a reduction of at least 50% from baseline in uPCR for the placebo group at week 26.			

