6.4. Analyses of Primary Efficacy Endpoint

The primary efficacy endpoint is the log-transformed ratio of uPCR at week 26 compared to baseline. The null $(H_{1,0})$ and alternative $(H_{1,1})$ hypotheses for the primary efficacy analysis are:

- H_{1,0}: There is no difference in log-transformed ratio of uPCR at week 26 compared to baseline between the pegcetacoplan and placebo treatment groups.
- H_{1,1}: There is a difference in log-transformed ratio of uPCR at week 26 compared to baseline between the pegcetacoplan and placebo treatment groups.

uPCR values are expected to be highly skewed so that the values will be natural log-transformed in analysis and presentation. For the primary efficacy endpoint, sensitivity analyses (Section 6.4.2), supplemental analyses (Section 6.4.3), and subgroup analyses (Section 6.4.4) will be performed.

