13.3. Definition of Baseline, RCP, and OLP

For all evaluations unless otherwise noted, baseline is defined as the most recent non-missing measurement prior to the first administration of study drug. Baseline can be the same date as first dose, given the measurement is expected prior to first dose when only date information is available.

In by-visit summary tables, the baseline will be summarized using all available data, but also for each visit using only the baseline data from participants with available data at the visit; hence the mean change from baseline will equal the mean visit value – mean baseline value.

Throughout this document 'change from baseline' refers to the actual change from baseline (ie, visit value – baseline value).

The date when a participant receives first administration of OLP drug will be defined as the start date of the participant's OLP, and that date minus one day will be the end date of the participant's RCP.

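### The sample code for the worst-change imputation after dialysis or transplant multiplies a log baseline by a percentage, where the SAP text implies adding a log change

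*SAP*

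**What the plan says.** For participants who start renal replacement therapy, Protocol Table 8, the notes to SAP Table 1 and SAP 6.4.1 all give the same rule. Later values are set to missing and imputed from the worst change among all participants and visits, with a random error. None of the three states a scale or a formula.

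Three other places bear on the scale:

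- SAP Table 1 summarises the primary estimand as "Difference in mean change of log-transformed uPCR from baseline to week 26".
- SAP 6.4 says of uPCR that "the values will be natural log-transformed in analysis and presentation".
- SAP 13.3 says that change from baseline, throughout the document, "refers to the actual change from baseline (ie, visit value – baseline value").

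The only formula is in the sample code of SAP 17.2.2: "if avisitn>startavisit>. then aval = base*(1+ worstpchg/100"), plus an error term. The comment under that line repeats it: "the 'base*(1+ worstpchg/100)' part is worst change". The data are selected in SAP 17.2.1 with "if paramcd = 'LNUPRCRF' and basetype = 'NORMAL' and", which is the log uPCR parameter. The error term is the imputed log value minus a visit average, described as "calculate the average log(uPCR) for each avisit". The model response is then the imputed value minus baseline.

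**The concern.** Every other quantity in that block is on the log scale and additive. A percentage factor applied to ln(uPCR) is not a change in ln(uPCR). It makes the imputed worsening depend on the recipient's own baseline and on whether uPCR is stored in mg/g or g/g, neither of which should matter to a worst-case log change. Because the comment restates the product, this is not a text-extraction slip.

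The rule sets primary-endpoint values for any participant who starts dialysis or has a transplant in the randomized period. The same imputed data set also feeds the slope code in SAP 17.2.3. SAP 6.5.3.1, 6.5.5.1, 6.6.4 and 6.6.5 refer back to the 6.4.1 handling for other continuous endpoints, so the missing definition is not confined to uPCR.

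There is a secondary point, subject to checking the source PDF for a lost equals sign. The code comment describes `startavisit` as "their first visit that should be imputed" by the worst change, but the printed condition is strictly greater than. As printed, that visit would keep its copy-reference value.

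**Working it through.** **Inputs from the documents.** Planning means -0.92 and -0.22, SD 0.88, 70 participants (SAP 3.4), so the planning difference is -0.22 - (-0.92) = 0.70. Enrolment 124 (protocol summary of changes). Entry uPCR at least 1000 mg/g (Protocol 7.1, criterion 5). Contrast weights 0.333, 0.333 and 0.334 for weeks 24, 25 and 26 (SAP 17.2).

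**Assumptions.** 62 per arm (124 split 1:1); baselines 1000 to 6000 mg/g; worst rise 2-, 4- or 10-fold; error averaging zero. Shifts are per affected participant.

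**1. The plan's own conversion.** ln(1 - 0.60) = -0.916 and ln(1 - 0.20) = -0.223, matching -0.92 and -0.22. At 35 per arm, SD 0.88 and 1-sided 0.025, power is 0.914 (0.907 by t-test), so at least 90% is confirmed. The SAP therefore converts a percentage p in uPCR to ln(1 + p/100), whatever the baseline.

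**2. The two rules.** Let D be the donor's worst log change, B_d the donor's log baseline and B_r the recipient's.

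- Additive rule: imputed change = D.
- Printed code with percentage w: imputed change = B_r × w/100. If w is the percentage change in ln(uPCR), w/100 = D/B_d, so imputed change = D × B_r/B_d. This equals D only when the two baselines are the same.

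**3. Percentage of ln(uPCR), mg/g.** ln 1000 = 6.908; ln 6000 = 8.700. The low end has the donor at 6000 and the recipient at 1000; the high end is the reverse.

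| Worst rise | D | Code, low to high | Shift in arm mean |
|---|---|---|---|
| 2-fold | 0.693 | 0.550 to 0.873 | -0.0023 to +0.0029 |
| 4-fold | 1.386 | 1.101 to 1.746 | -0.0046 to +0.0058 |
| 10-fold | 2.303 | 1.828 to 2.900 | -0.0076 to +0.0096 |

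Example: 1.386/6.908 × 8.700 = 1.746, and (1.746 - 1.386)/62 = 0.0058. Against 0.70, the largest shifts are 0.8% (4-fold) and 1.4% (10-fold).

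**4. Unit dependence.** Take the same 4-fold rise in g/g with the donor at 2 g/g: w/100 = 1.386/0.693 = 2.

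- Recipient at 1 g/g: ln 1 = 0, so imputed change 0; shift (0 - 1.386)/62 = -0.022 (-3.2%).
- Recipient at 6 g/g: 2 × 1.792 = 3.584; shift (3.584 - 1.386)/62 = +0.035 (+5.1%).

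**5. Percentage of raw uPCR (less likely reading).** A 4-fold rise is +300%, giving 3 × 6.908 = 20.7 to 3 × 8.700 = 26.1 as a log change, which is impossible.

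**6. Skipped visit, if the condition is as printed.** The weight on worst-change values in the week 24-26 contrast falls from 1 to 0.667, from 0.667 to 0.334, or from 0.334 to 0 when the first affected visit is week 24, 25 or 26. There is no effect if it is week 20 or earlier. For a 4-fold rise, with a retained copy-reference change assumed between -0.22 and +0.69:

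- 0.333 × (1.386 + 0.22) = 0.535; /62 = 0.0086; /0.70 = 1.2%.
- 0.333 × (1.386 - 0.693) = 0.231; /62 = 0.0037; /0.70 = 0.5%.

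**The case against.** SAP 17.2 labels the code as examples that may need changes to reflect the SAP's methods, so the text ranks above it. The block is partly pseudo-code and cannot run verbatim: its closing transpose omits the imputation identifier from the BY list, so a programmer has to rework it. The additive rule is inferred, since the rule itself names no scale and the comments speak of a percentage. The effect is small on the likely reading. The main uPCR cut in SAP 6.4.4 is in mg/g; g/g appears only in a descriptive shift table in SAP Addendum 6.7.1. As described, the MAR and tipping-point sensitivity analyses and the per-protocol analysis do not use this step. A SAP edit made after the results were reported is not prespecification.

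Much of this stands, and it limits the size of the point: the g/g figures only illustrate unit dependence, the skipped visit needs the PDF, and the effect may be nil. It does not remove the error. No other place defines the worst change or the random error, so a programmer who turns to the SAP for a formula finds only this one, and it disagrees with the scale used everywhere else. Analyses that bypass the step offer a comparison but do not correct the primary analysis.

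**Conclusion.** The point holds: as printed, the formula does not produce a worst change on the scale of the primary endpoint, whichever way the percentage was calculated. It should be fixed, though the numerical stake is probably small. On the likely mg/g reading, one affected participant moves an arm mean by under 1% of the planning difference for a 4-fold rise and by at most 1.4% for a 10-fold rise. This rests on the assumed baselines, rises and arm size. The effect would be larger in g/g, and the values would be impossible if raw percentages were used. If nobody started dialysis or had a transplant in the randomized period, nothing changes. The documents give no event count and do not show which code was run.

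**What to change.** - In SAP 6.4.1, state that for uPCR the worst change is the maximum, over participants and visits in the observed (non-imputed) data, of ln(uPCR at visit) minus ln(baseline).
- In SAP 17.2.2, code the imputed value as log baseline + worst log change + (imputed value - visit average). Define the visit average as that participant's mean at that visit over the 100 imputations, so that the error averages zero.
- Make the visit condition greater than or equal to `startavisit`.
- SAP Addendum section 11 says the randomized-period results are in a CSR dated 05 December 2024. So first count dialysis and transplant events in that period. If there were any, confirm which code was run, and rerun the primary analysis if it followed the printed lines. Report any such rerun as a correction made after the results were known.

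The cost is one SAP sentence, two code lines and a one-line definition. A rerun is needed only if an event occurred and the printed code was used.
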